### 8.14. Exposure During Pregnancy

For both unapproved/unlicensed products and for marketed products, an exposure during pregnancy occurs if:

1. A female becomes, or is found to be, pregnant either while receiving or having been exposed (eg, because of treatment or environmental exposure) to the investigational product; or the female becomes or is found to be pregnant after discontinuing and/or being exposed to the investigational product;

2. An example of environmental exposure would be a case involving direct contact with a Eloxx Pharmaceuticals product in a pregnant woman (eg, a nurse reports that she is pregnant and has been exposed to chemotherapeutic products).
3. A male has been exposed (eg, because of treatment or environmental exposure) to the investigational product prior to or around the time of conception and/or is exposed during his partner's pregnancy.

If a study subject or study subject's partner becomes or is found to be pregnant during the study subject's treatment with the investigational product, the Investigator must submit this information to the CRO on a pregnancy form. In addition, the Investigator must submit information regarding environmental exposure product in a pregnant woman (eg, a subject reports that she is pregnant and has been exposed to a cytotoxic product by inhalation or spillage). This must be done irrespective of whether an AE has occurred and within 24 hours of awareness of the exposure. The information submitted should include the anticipated date of delivery (see below for information related to termination of pregnancy).

Follow-up is conducted to obtain general information on the pregnancy and its outcome. The Investigator will follow the pregnancy until completion (or until pregnancy termination) and notify the CRO and Eloxx Pharmaceuticals of the outcome as a follow-up by forwarding the completed pregnancy form B. In the case of a live birth, the structural integrity of the neonate can be assessed at the time of birth. In the event of a termination, the reason(s) for termination should be specified and, if clinically possible, the structural integrity of the terminated fetus should be assessed by gross visual inspection (unless preprocedure test findings are conclusive for a congenital anomaly and the findings are reported).

Follow-up is conducted to obtain general information on the pregnancy and its. The Investigator will follow the pregnancy until completion (or until pregnancy termination) and notify the CRO and Eloxx Pharmaceuticals of the outcome as a follow-up by forwarding the completed pregnancy form B. In the case of a live birth, the structural integrity of the neonate can be assessed at the time of birth. In the event of a termination, the reason(s) for termination should be specified and, if clinically possible, the structural integrity of the terminated fetus should be assessed by gross visual inspection (unless preprocedure test findings are conclusive for a congenital anomaly and the findings are reported).

If the outcome of the pregnancy meets the criteria for an SAE (ie, ectopic pregnancy, spontaneous abortion, intrauterine fetal demise, neonatal death, or congenital anomaly [in a live-born baby, a terminated fetus, an intrauterine fetal demise, or a neonatal death]), the Investigator should follow the procedures for reporting SAEs.

Additional information about pregnancy outcomes that are reported as SAEs follows:

- Spontaneous abortion includes miscarriage and missed abortion;
- Neonatal deaths that occur within 1 month of birth should be reported, without regard to causality, as SAEs. In addition, infant deaths after 1 month should be reported as SAEs when the Investigator assesses the infant death as related or possibly related to exposure to the investigational product.

Additional information regarding the exposure during pregnancy (EDP) may be requested by the Investigator. Further follow-up of birth outcomes will be handled on a case-by-case basis

(eg, follow-up on preterm infants to identify developmental delays). In the case of paternal exposure, the Investigator will provide the study subject with the Pregnant Partner Release of Information Form to deliver to his partner. The Investigator must document in the source documents that the subject was given the Pregnant Partner Release of Information Form to provide to his partner.

### **8.15. Follow-up of Adverse Events**

Subjects who have had an AE during the treatment period must be followed clinically until all parameters (including laboratory) have either returned to normal or have stabilized or are otherwise explained.

Any newly emergent SAE within 30 days after early discontinuation or study completion, that is considered to be related to the test drug or study participation should be recorded and reported immediately. The post-study period for the purpose of SAE reporting is until the SAE is resolved or stabilized or maximum up to 30 days following last visit of the study.

Unless decided otherwise, the study will terminate 30 days after last subject has attended the End-of Study visit. If additional follow-up of an AE is warranted, it will be documented in the as the subject' source data but will not be part of the CRF. The PI is required to report on any significant findings to the Sponsor.

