- If an HFA ototoxic event occurs in 2 subjects receiving ELX-02 in any cohort, 6 subjects receiving ELX-02 and 3 subjects receiving placebo will be added to the current dose level, unless it is determined by the Sponsor and the AVDSMB, following a thorough medical review, that the study may resume. In this instance additional subjects will not need to be added.

- If an HFA ototoxic event occurs in  $\geq 3$  subjects receiving ELX-02 in any cohort, this will be considered a DLT and dose escalation to the next dose level will not be authorized. The previous dose level will be determined as the MTD.

If the criteria for stopping a dose has been met for an individual subject during a cohort, the study may be temporarily suspended immediately to allow for further medical evaluation with additional assessments of the propted event, as appropriate. If any subject/subjects meet dose stopping or significant change criteria, the sponsor, after discussion with PI, may pause the study for another careful review of data for all subjects; Study may be resumed for the remaining subjects after discussions between the sponsor and site, taking into consideration the safety surveillance of the discontinued participants, as well as, the dosed ones. If this occurs, the following process will be initiated:

- Subjects will continue their participation with the same dose in order to assure that all subjects receive their entire complement of nine doses per cohort.
- Subjects who have received the required number of injections for a dose on a dosing day prior to study suspension will continue with their next administration, regardless of the treatment day, in order to receive their total of 9 doses per cohort.
- Subjects who did not receive the required number of injections on a dosing day prior to study suspension will not need to repeat that dosing day, they will proceed to the next administration, regardless of the treatment day, in order to receive their total of

nine doses per cohort.

The discontinued subjects who met the significant change or dose stopping criteria will be followed for safety and surveillance audiology tests; the monitoring period will continue either until the resolution of the event, such time that it is determined that changes are permanent or the subject is lost to follow-up. The determination for permanency will be made by the AVDSMB and does not have a specified time frame.

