##### **5. Tinnitus questionnaire (Tinnitus Handicap Inventory).**

If a subject has a score of a 5 point increase in THI score from baseline accompanied by a shift in Grade (eg from Grade 1 to Grade 2), the event will be discussed between the Investigator, the medically-qualified sponsor representative and the medically-qualified sponsor representative and the adjudication committee to determine if further auditory testing will be required. Any findings consistent with drug-induced toxicity leading to tinnitus on formal evaluation will be re-evaluated 3 months after initial exam and, if persistent, will be deemed permanent.

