#### 6. Vestibular questionnaire (Dizziness Handicap).

If a subject has a score of 31 or greater on the DHI accompanied by a 5 point increase from baseline and an associated shift in category (eg from mild to moderate handicap), the event will be discussed between the Investigator, the medically-qualified sponsor representative and the adjudication committee to determine if further vestibular testing will be required. Any findings consistent with drug-induced vestibular toxicity on formal evaluation will be re-evaluated 3 months after initial exam and, if persistent, will be deemed permanent.

For both the PTA and HFA:

The Significant Change Criteria as defined by American Speech-Language-Hearing Association (ASHA) and American Academy of Audiology (AAA) will be used to trigger a review when the thresholds are worse by the following criteria:

- $\geq 20$  dB change at any frequency,
- $\geq 10$  dB change at any 2 adjacent frequencies, or
- loss of response at 3 consecutive frequencies where responses were obtained at baseline.

To be considered significant as an early warning for possible ototoxicity, changes showing a worsening meeting the above criteria must replicate 24 hours later with no indication of middle ear abnormality. Subjects serve as their own controls for ototoxic change, which is computed relative to baseline measures.

Abnormal tests should be repeated within 24 hours, preferably immediately (with the exception of the questionnaires). For all tests, the same equipment should be used for the screening and EOS, as well as any repeat test to minimize technical variability. If any of the tests meet the significant change criteria described above, this finding must be considered an ototoxic AE (“Adverse Event of Interest”), which must be reported immediately to the the Medical Monitor and the Sponsor. The Sponsor will update the DSMB and AVDSMB.

We define reverse ASHA significant change criteria as an improvement, rather than a worsening by the same amount of change. Reverse ASHA significant change criteria will be used only as a measure of variability or possible learning effect as the subject becomes more experienced in the test procedures.

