3.10. Missing, Unused, and Spurious Data

In general, there will be no substitutions made to accommodate missing data points, other than described in this section. All data recorded on the eCRF will be included in data listings.

When tabulating AE data, partial dates will be handled as follows. If the day of the month is missing, the onset day will be set to the first day of the month unless it is the same month and year as study treatment. In this case, in order to conservatively report the event as treatment-emergent, the onset date will be assumed to be the date of first dose. If the onset day and month are both missing, the day and month will be assumed to be January 1, unless the event occurred in the same year as the study treatment. In this case, the event onset will be coded to the date of first dose in order to conservatively report the event as treatment-emergent. A missing onset date will be coded as the date of first dose. If the resulting onset date is after a reported date of resolution, the onset date will be set equal to the date of resolution. Imputation of partial dates is used only to determine whether an event is treatment-emergent; data listings will present the partial date as recorded in the eCRF.

Missing AE severities will not be imputed and will be considered missing in any tabulations of AE severity. When relation of AE to the study drug is missing, the AE will be considered “related” to study drug.

When tabulating concomitant medications, if an end date is missing or the medication is ongoing at the time of first dose, the medication will be considered concomitant.

All final PK parameters will be calculated based on actual time from dose. Interim PK parameters may be calculated based upon scheduled time if actual time data are not yet available.

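### The protocol plans a 3-month check for permanent tinnitus or vestibular toxicity, but its default study end and CRF rule do not ensure that the result reaches the CRF or the SAP outputs

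*Protocol*

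**What the plan says.** Four protocol passages govern how long an ear or balance event is followed and where the result is kept.

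- **Section 8.4.2, items 5 and 6.** Tinnitus findings consistent with drug toxicity on formal evaluation are "re-evaluated 3 months after initial exam and, if persistent, will be deemed permanent". The vestibular item uses the same rule: such findings "will be re-evaluated 3 months after initial exam and, if persistent, will be deemed permanent".
- **Section 3.2.** Discontinued subjects who met the significant-change or dose-stopping criteria stay under audiology surveillance. "The determination for permanency will be made by the AVDSMB and does not have a specified time frame".
- **Section 8.15.** "Unless decided otherwise, the study will terminate 30 days after last subject has attended the End-of Study visit". Additional follow-up of an adverse event is documented as "source data but will not be part of the CRF".
- **Section 8.20.** All adverse events are documented in eSource and followed until they resolve or stabilise, or until final database lock.

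Section 7.3.1 collects adverse events up to the EOS visit. On the analysis side, SAP Section 3.10 states: "All data recorded on the eCRF will be included in data listings". SAP Section 4.4.6 has no auditory or vestibular visit after EOS. SAP Sections 4.4.2, 4.4.3, 4.4.6.5 and 4.4.6.6 plan no summary of adverse event outcome or permanence.

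**The concern.** The protocol plans an examination whose stated purpose is to decide whether a tinnitus or vestibular toxicity is permanent. It then sets a default closing date that comes before that examination for the last subject, and directs additional follow-up away from the CRF. This is an explicit rule acting on a planned safety result, so it is more than an omission.

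Ototoxicity is a known aminoglycoside risk (Protocol Section 1.1.1) and a named adverse event of interest (Section 8.4). The first primary endpoint covers the characteristics of adverse events as well as their incidence, and reversibility is an important characteristic of an ototoxic event. Section 8.7 lists permanent impairment of a body function under serious injury, so the 3-month result can also bear on how an event is classified. The last cohort is the one given the highest dose, 5.0 mg/kg (SAP Section 1.2.1), and it has the least calendar time before closure.

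**Working it through.** **Inputs**

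- Last dose: Day 29 (Protocol Section 3.1).
- EOS visit: 7-10 days after the last dose. EOS auditory and vestibular tests: 7-11 days after it (Section 7.1).
- First on-study auditory and vestibular exam: Day 3, allowed one day early, so Day 2-3 (Section 3.1).
- Default study end: last EOS visit + 30 days (Section 8.15).
- Permanence re-evaluation: initial exam + 3 months (Section 8.4.2), taken here as 90-92 days.
- Cohort spacing: at least 14 days after the previous cohort's last dose (Section 3.2).

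**The plan's own figure.** EOS = 29 + 7 = Day 36, as stated in Section 7.1. The window runs to 29 + 10 = Day 39, and the EOS hearing tests to 29 + 11 = Day 40.

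**Default closure, last subject.** 36 + 30 = Day 66, to 39 + 30 = Day 69.

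**Default closure on the Cohort 6 calendar at minimum spacing.** Cohort 7 Day 1 is Cohort 6 Day 29 + 14 = Day 43, a shift of 42 days. Closure is therefore 66 + 42 = Day 108, to 69 + 42 = Day 111.

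**Re-evaluation day** = exam day + 90 to 92. Days late = re-evaluation day minus closure day. The smallest value pairs the earliest re-evaluation with the latest closure, and the largest does the reverse.

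| First exam | Re-evaluation | Last subject, closure Day 66-69 | Cohort 6, closure Day 108-111 |
|---|---|---|---|
| Day 2-3 | Day 92-95 | 23-29 days late | 13-19 days early |
| Day 10 | Day 100-102 | 31-36 days late | 6-11 days early |
| Day 17 | Day 107-109 | 38-43 days late | 4 days early to 1 day late |
| Day 24 | Day 114-116 | 45-50 days late | 3-8 days late |
| EOS, Day 36-40 | Day 126-132 | 57-66 days late | 15-24 days late |

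The extremes for the last subject are 92 - 69 = 23 and 132 - 66 = 66.

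**Latest first exam that fits.** In Cohort 6 at minimum spacing it lies between 108 - 92 = Day 16 and 111 - 90 = Day 21, so a finding first examined from Day 22 on always misses. For the last subject the most favourable case is 69 - 90 = Day -21, which is during screening, so no on-study finding fits.

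**Staggered enrolment in Cohort 7.** An earlier subject's result would fit only if the last subject's schedule ran about 23-29 days later (Day 2-3 finding) or 57-66 days later (EOS finding). The documents state no stagger.

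**Reading of additional follow-up in Section 8.15.** If it means follow-up after study end, the table applies. If it means anything after a subject's own EOS visit, which Section 7.3.1 supports, then even the earliest re-evaluation (Day 92) comes after EOS (Day 36-39), and every cohort is affected.

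**The case against.** A reader might infer that permanence of events in the 5.0 mg/kg cohort cannot reach the analysis at all. The documents do not support that. Section 8.15 allows a different end date. Section 8.20 follows adverse events to resolution, stabilisation or lock through eSource, and Section 11.4 transfers the required eSource data to the clinical database. Section 11.6 fixes no lock date and permits authorised updates after lock. Section 3.2 sets no time limit on the AVDSMB's permanency decision. Nor can one say that all last-cohort events miss closure, because that would need joint dosing, which is not stated.

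There are also other channels. Section 8.15 has the investigator report significant findings to the sponsor. Section 8.21.1 follows serious events with permanent impairment until they stabilise, although Section 8.15 caps the post-study SAE period at 30 days after the last visit. Section 11.11.1 allows report narratives. Section 8.20 concedes that certain long-term events cannot be followed to resolution within the study. The event, its grade and its causality are recorded in any case. Because the SAP plans no permanence summary, no planned analysis is lost.

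These points rule out an absolute claim but do not settle the conflict. The option of a later end date names no trigger and no consequence for the CRF. Lock takes place once the database is considered clean, which gives no minimum date. Reports to the sponsor and optional narratives do not put a permanence result into the CRF or the SAP outputs. The 8.20 concession concerns events that cannot be followed to resolution, whereas the 3-month examination is one that the protocol itself plans.

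One limit of scope stands in full. The 3-month rule covers tinnitus and vestibular findings. Hearing-threshold shifts do not fall under it; in discontinued subjects they fall under the open-ended rule in Section 3.2.

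**Conclusion.** Capture of the permanence result in the CRF and the SAP outputs is not ensured. On the default dates, the 3-month result for the last subject falls about 23 to 66 days after study end, whichever on-study exam first showed the finding. At minimum cohort spacing, Cohort 6 findings first examined from Day 22 on miss closure too. All cohorts are affected if additional follow-up starts at each subject's own EOS visit.

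This rests on 3 months being 90-92 days, on the initial exam being the first on-study evaluation of the finding, and on the 30-day default being applied. If formal evaluation comes later than the questionnaire that prompted it, the gap grows. Reading the initial exam as one at screening, on or before about Day -21, would close the gap but is implausible for a drug-induced finding.

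The practical effect depends on a confirmed tinnitus or vestibular toxicity still being open at study end, in cohorts with six subjects on active drug. Such an event may be rare, but it would bear directly on reversibility of the main class risk, and the remedy is cheap. It should be fixed.

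**What to change.** Reconcile Protocol Sections 3.2, 8.4.2, 8.15 and 8.20 on data capture:

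1. In Section 8.15, exempt ear and labyrinth adverse events of interest from the CRF exclusion, so that the 3-month re-evaluation already planned and any AVDSMB permanency decision are recorded. State whether additional follow-up is counted from the subject's EOS visit or from study end.
2. In the SAP, add a by-subject listing of the permanence outcome for these events: resolved, permanent, or pending at lock.
3. Report results still pending at lock in a dated addendum. Do not hold the lock open, since the AVDSMB decision has no time limit.

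The cost is one CRF page, a sentence or two in each document, and possibly a short addendum. The SAP already lists the doses given in all seven cohorts, so a protocol amendment may come late. In that case the SAP listing and addendum, drawing on source data, are the workable part. No change to the clinical follow-up itself is proposed.

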### **8.16. Independent Data and Safety Monitoring Board (DSMB)**

A DSMB for the study will be formed to review the safety information generated for each cohort' subjects upon their completion of all EOS assessments.

The DSMB will be composed of four independent physicians specialized in relevant medical fields who will monitor general events. In addition, a separate Auditory and Vestibular DSMB composed of two ENT specialists will monitor and assess events which may be ototoxic in nature. The Sponsor's medically qualified representative and the Investigator and/or designee may attend the DSMB's open sessions but are not allowed to vote.

The primary responsibility of the DSMB is to evaluate the safety data collected for all subjects in the recently completed cohort and the safe conduct of the study and provides the Sponsor with a report summarizing the conclusions of the meeting, and its recommendation whether to proceed to the next cohort or otherwise. The decision to proceed to a higher dose level will be made by the Sponsor after considering the DSMB's, the advice of the AVDSMB, and the PI's recommendation following the safety assessments and based on the dose-escalation stopping rules (Section 3.2).

Dose escalation will be permitted if the prior dose was well tolerated, if there were no safety or tolerability concerns. The next cohort will be dosed at least 14 days after the last dosing in the previous group. This window between cohort's dosing can be extended in case the DSMB request for additional information to support its conclusion regarding the previous dose safety profile.

DSMB working procedures will be described in a DSMB charter prior to enrolling the first subject. The DSMB will prepare a report of its recommendations and will forward it to the Sponsor. The Sponsor will forward such decisions, which may include summaries of aggregate analyses of endpoint events and of safety data that are not endpoints, to regulatory authorities, as appropriate.

### **8.17. Occupational Exposure**

An occupational exposure occurs when, during the performance of job duties, a person (whether a healthcare professional or otherwise) gets in unplanned direct contact with the product, which may or may not lead to the occurrence of an AE.

An occupational exposure is reported to the drug safety unit within 24 hours of the Investigator's awareness, using the SAE report form, regardless of whether there is an associated AE/SAE. Since the information does not pertain to a subject enrolled in the study, the information is not reported on a CRF; however, a copy of the completed SAE report form is maintained in the Investigator site file.

